5.4 Study Endpoints

5.4.1 Primary Endpoints

5.4.1.1 Primary Safety Endpoint

The primary safety endpoint of the study is **combined safety** at 30 days, defined according to modified VARC-2¹ ("TAVI early safety") as the composite of:

- All-cause mortality
- All stroke (disabling and non-disabling)
- Life-threatening or disabling bleeding
- Acute kidney injury – Stage 2 or 3 (including renal replacement therapy)
- Coronary artery obstruction requiring intervention

- Major vascular complication
- Valve-related dysfunction requiring repeat procedure (BAV, TAVI, or SAVR)

5.4.1.1.2 Primary Efficacy Endpoint- **Phase II**

The primary efficacy endpoint of the study is the **hierarchical composite efficacy endpoint**, determined by pair-wise comparisons among all subjects according to the following pre-specified hierarchy of adverse outcomes:

- All-cause mortality and/or any stroke (fatal and non-fatal, disabling or non-disabling) [evaluated at 30 days]
 - If both had a death/stroke, a time to event analysis by days will determine a win
 - If both patients had a stroke at the same day the comparison moves to the next tier
- NIHSS worsening (increase from baseline) [evaluated at 2 to 5 days post-procedure]
- Freedom from any cerebral ischemic lesions detected by diffusion-weighted magnetic resonance imaging (DW-MRI) 2 to 5 days post-procedure
- Total volume of cerebral ischemic lesions detected by diffusion-weighted magnetic resonance imaging (DW-MRI) 2 to 5 days post-procedure.

Each subject in the intervention group will be compared with each and every subject from the control group based on the above hierarchy according to the Finkelstein-Schoenfeld method.² For example, if Subject A dies or has stroke and Subject B survives free of stroke to 30 days, Subject B wins (score +1) and Subject A loses (score -1). If both subjects die or both have a stroke on the same day, it is equilibrium (score 0). If both subjects survive free of stroke to 30 days, the comparison moves to the next tier of the hierarchy. A lack of an event is given a +1 score. An event which is less severe than the comparison gets a 0 score (for example death vs. stroke)

After all between-subject comparisons have been performed, scores are summed to obtain a cumulative score for each subject, and outcomes between treatment groups are then compared.

5.4.2 Secondary Endpoints

5.4.2.1.1 Hypothesis-driven secondary endpoints

For the following secondary endpoints, a test for superiority of each intervention group to the control group will be performed. To address the issue of multiple tests among these secondary endpoints, sequential testing is planned. Secondary endpoints will be formally tested if and only if the primary study hypotheses are confirmed. The secondary endpoints will be tested individually, in the order in which they are listed as follows:

- **All stroke** [evaluated at 7 days in the eITT population]
- **NIHSS worsening**, defined as any NIHSS score increase from baseline [evaluated at 2 to 5 days post-procedure in the efficacy Intention to Treat (eITT) analysis population]. A sensitivity analysis will further compare ≥ 2 points NIHSS worsening [evaluated at 2-5 days post-procedure in the efficacy Intention to Treat (eITT) analysis population]
- **Composite of all-cause mortality and all stroke** [evaluated at 7 days in the eITT population]

- **CNS Infarction** (NeuroARC defined) [evaluated at 30 days in the eITT analysis population]
- **Total volume of cerebral ischemic lesions** detected by DW-MRI, [evaluated 2 to 5 days post-procedure in the efficacy Intention to Treat (eITT) analysis population]

The above endpoints will be tested by this pre-specified sequence, until the first non-significant difference is found between the two treatment groups. After that, other treatment comparisons will be examined in an exploratory manner.

5.4.2.1.2 Secondary Safety Endpoints

The following safety endpoints will be evaluated in-hospital and at 30 days. Overall event rates will be reported by treatment group. In the Intervention and Roll-In groups, all safety endpoints will be adjudicated for their relationship to the investigational device and/or the investigational procedure by an independent Clinical Events Committee (§11.1):

- In-hospital procedural safety, defined as the composite of the following Major Adverse Cardiovascular and Cerebrovascular Events (MACCE):
 - All-cause mortality
 - All stroke (disabling and non-disabling)
 - Life threatening (or disabling) bleeding
 - Acute kidney injury – Stage 2 or 3 (including renal replacement therapy)
 - Major vascular complications
- TAVI device success (VARC), evaluated in-hospital, defined as:
 - Absence of procedural mortality AND
 - Correct positioning of a single prosthetic heart valve into the proper anatomical location AND
 - Intended performance of the prosthetic heart valve (no prosthesis-patient mismatch (VARC-defined) and mean aortic valve gradient <20 mm Hg or peak velocity <3 m/s, AND no moderate or severe prosthetic valve regurgitation (VARC-defined) (site-reported)
- General safety, defined as the composite of the following adverse events (each VARC-2 defined):
 - All-cause mortality
 - All stroke (disabling and non-disabling)
 - Acute kidney injury – Stage 3 (including renal replacement therapy)
- Mortality [evaluated in-hospital and at 30 and 90 days]:
 - All-cause mortality
 - Cardiovascular mortality

- Neurologic event related mortality
 - Non-cardiovascular mortality
- Myocardial infarction:
 - Peri-procedural MI (≤ 72 hours after the index procedure)
 - Spontaneous MI (> 72 hours after the index procedure)
- Neurological Events (component and composite):
 - Stroke (VARC-2 defined) **[evaluated in-hospital and at 30 and 90 days]**
 - Ischemic stroke
 - Hemorrhagic stroke
 - Undetermined
 - Disabling Stroke (VARC-2 defined) **[evaluated in-hospital and at 30 and 90 days]**
 - Non-disabling stroke (VARC-2 defined) **[evaluated in-hospital and at 30 and 90 days]**
 - Transient ischemic attack (TIA) (VARC-2 defined)
 - Overt CNS Injury (NeuroARC defined Type 1) **[evaluated in-hospital and at 30 and 90 days]**
 - Covert CNS Injury (NeuroARC defined Type 2)
 - Neurological dysfunction without CNS injury (NeuroARC defined Type 3)
 - CNS infarction (NeuroARC defined composite neurological endpoint)
 - CNS hemorrhage (NeuroARC defined composite neurological endpoint)
- Bleeding Complications:
 - Life-threatening bleeding (VARC-2)
 - Major bleeding
 - Minor bleeding
- Acute Kidney Injury (AKIN Classification):
 - Stage 2
 - Stage 3
- Vascular Complications:
 - Major vascular complications
 - Major vascular complications related to device

5.4.2.1.3 Secondary Efficacy Endpoints

5.4.2.1.4 Phase I: Hierarchical composite efficacy endpoint, determined by pair-wise comparisons among all subjects according to the following pre-specified hierarchy of adverse outcomes:

- All-cause mortality or any stroke (disabling or non-disabling) [evaluated at 30 days]
- NIHSS worsening (increase from baseline) [evaluated at 2-5 days post-procedure] or Montreal Cognitive Assessment worsening (decrease of 3 or more points from baseline) [evaluated at 30 days]
- Total volume of cerebral ischemic lesions detected by diffusion-weighted magnetic resonance imaging (DW-MRI) 2 to 5 days post-procedure

Each subject in the intervention group will be compared with each and every subject from the control group based on the above hierarchy according to the Finkelstein-Schoenfeld method.² For example, if Subject A dies or has stroke and Subject B survives free of stroke to 30 days, Subject B wins (score +1) and Subject A loses (score -1). If both subjects die or have a stroke, it is equilibrium (score 0). If both subjects survive free of stroke to 30 days, the comparison moves to the next tier of the hierarchy.

After all between-subject comparisons have been performed, scores are summed to obtain a cumulative score for each subject, and outcomes between treatment groups are then compared.

5.4.2.1.5 Imaging Efficacy Endpoints (Phase I and Phase II):

- Presence of cerebral ischemic lesions detected by DW-MRI, evaluated 2 to 5 days post-procedure
- Number of cerebral ischemic lesions detected by DW-MRI, evaluated 2 to 5 days post-procedure
- Per-patient average single cerebral ischemic lesion volume detected by DW-MRI, evaluated 2 to 5 days post-procedure
- Single cerebral ischemic lesion volume (lesion-level analysis) detected by DW-MRI, evaluated at 2 to 5 days post-procedure
- Total volume of cerebral ischemic lesions detected by DW-MRI, evaluated 2 to 5 days post-procedure

5.4.2.1.6 Neurologic Efficacy Endpoints (Phase I and Phase II):

- NIHSS worsening, defined as an NIHSS score increase from baseline [baseline score compared with score evaluated at 2-5 days post-procedure and at 30 days]
- New neurologic impairment, defined as an NIHSS score increase from baseline accompanied by the presence of cerebral ischemic lesions [evaluated at 2-5 days post-procedure and at 30 days]

5.4.2.1.7 Secondary Performance Endpoints

The following performance endpoints will be evaluated post-procedure in the Intervention group (Roll-Ins excluded). TriGuard HDH and TriGUARD 3 reported individually:

- Successful device deployment, defined as ability to access the aortic arch with the TriGuard HDH or TriGUARD 3 delivery catheter and deploy the device from the delivery catheter into the aortic arch
- Successful device positioning, defined as ability to position the TriGuard HDH or TriGUARD 3 device in the aortic arch to cover all major cerebral arteries, with proper positioning maintained (verified by fluoroscopy) until the following time points:
 - Final deployment of the first prosthetic valve
 - Final procedure (after any additional post-dilatation or additional valve implantations have been completed, and the TAVR delivery system has been removed)
- Extent of cerebral artery coverage will be reported as:
 - Complete (coverage of all 3 cerebral artery branches)
 - Partial (coverage of 1-2 cerebral artery branches)
 - None

Note: Maintenance of device positioning to each time point and extent of cerebral artery coverage will be evaluated by the Angiographic Core Laboratory.

- Device interference, defined as interaction of the TriGuard HDH or TriGUARD 3 device with the TAVI system leading to:
 - Inability to advance or manipulate the TAVI delivery system or valve prosthesis, OR
 - Inability to deploy the TAVI valve prosthesis, OR
 - Inability to retrieve the valve prosthesis or delivery system
- Successful device retrieval, defined as ability to retrieve the TriGuard HDH or TriGUARD 3 CEPD.
- Technical success, defined as successful device deployment, device positioning, and successful device retrieval in the absence of device interference
- Procedure success, defined as technical success in the absence of any investigational device-related or investigational procedure-related in-hospital procedural safety events

5.4.3 Other Measures

The following additional measures will also be evaluated (TriGuard HDH and TriGUARD 3 reported individually):

5.4.3.1.1 Device deployment time – Time elapsed between insertion of the TriGuard HDH or TriGUARD 3 device into the groin access point and successful device deployment [evaluated post-procedure]

5.4.3.1.2 Total procedural time – Time elapsed between first arterial access and removal of the last catheter from the arterial access sheath [evaluated post-procedure]

5.4.3.1.3 Total fluoroscopy time [evaluated post-procedure]

5.4.3.1.4 Total contrast utilization [evaluated post-procedure]

6.0 Study Conduct

6.1 Enrollment Criteria

6.1.1 General Inclusion Criteria

Subjects must meet ALL of the following criteria to be eligible for enrollment into the study:

6.1.1.1.1 The patient is a male or non-pregnant female ≥ 18 years of age

6.1.1.1.2 The patient meets indications for TAVI

6.1.1.1.3 The patient is willing to comply with protocol-specified follow-up evaluations

6.1.1.1.4 The patient, or legally authorized representative, has been informed of the nature of the study, agrees to its provisions and has provided written informed consent, approved by the appropriate Institutional Review Board (IRB) or Ethics Committee (EC)

6.1.2 General Exclusion Criteria

Potential subjects will be excluded if ANY of the following criteria apply:

6.1.2.1.1 Patients undergoing TAVI via the trans- apical, trans -axillary, trans-subclavian, or trans-aortic route (applicable to Phase II)

6.1.2.1.2 Patients undergoing TAVI via the transapical approach due to friable or mobile atherosclerotic plaque in the aortic arch (*Phase I only*)

6.1.2.1.3 Patients with a previously implanted prosthetic aortic valve (i.e., planned valve-in-valve TAVI)

6.1.2.1.4 Pregnant or nursing subjects and those who plan pregnancy in the period up to 1 year following index procedure. Female subjects of child-bearing potential must have a negative pregnancy test done within 14 days prior to index procedure per site standard test.

6.1.2.1.5 Patients with known diagnosis of acute myocardial infarction (AMI) within 72 hours preceding the index procedure (according to definition) or AMI >72 hours preceding the index procedure, in whom CK and CK-MB have not returned to within normal limits at the time of procedure, or patients who are currently experiencing clinical symptoms consistent with new-onset AMI, such as nitrate-unresponsive prolonged chest pain.

6.1.2.1.6 Patients with a history of bleeding diathesis or coagulopathy or patients in whom anti-platelet and/or anticoagulant therapy is contraindicated, patients who will refuse transfusion, or patients with an active peptic ulcer or history of upper gastrointestinal (GI) bleeding within the prior 3 months.

6.1.2.1.7 Patients with known mental or physical illness or known history of substance abuse that may cause non-compliance with the protocol, confound the data interpretation, or is associated with a life expectancy of less than one year

6.1.2.1.8 Patients with severe allergy to heparin or known hypersensitivity or contraindication to aspirin, heparin/bivalirudin, clopidogrel, nitinol, stainless steel alloy, and/or contrast sensitivity that cannot be adequately pre-medicated

6.1.2.1.9 Patients with a history of a stroke or transient ischemic attack (TIA) within the prior 6 months

6.1.2.1.10 Patients with renal failure (estimated Glomerular Filtration Rate [eGFR] <30 mL/min, calculated from serum creatinine by the Cockcroft-Gault formula or MDRD- Modification of Diet in Renal Disease formula)

6.1.2.1.11 Patients with hepatic failure (Child-Pugh class C)

6.1.2.1.12 Patients with hypercoagulable states that cannot be corrected by additional periprocedural heparin

6.1.2.1.13 Patients presenting with cardiogenic shock at the time of the index procedure

6.1.2.1.14 Patients with severe peripheral arterial, abdominal aortic, or thoracic aortic disease that precludes delivery sheath vascular access

6.1.2.1.15 Patients in whom the aortic arch (*Phase I and II*), innominate artery ostium (*Phase I only*), or proximal innominate artery (*Phase I only*) are heavily calcified, severely atheromatous, or severely tortuous

6.1.2.1.16 Patients with an innominate artery ostium diameter <10 mm or >25 mm (*Phase I only*)

6.1.2.1.17 Patients with a transverse aortic diameter >43 mm (*Phase I only*)

6.1.2.1.18 Patients with anatomic irregularities of the innominate artery that could prevent positioning of the TriGuard upper stabilizer and compromise stability of the device (*Phase I only*)

6.1.2.1.19 Patients with any other condition that would prevent adherence to the TriGuard HDH (Phase I) or TriGUARD 3 (Phase II) Instructions for Use

6.1.2.1.20 Patients with contraindication to cerebral MRI

6.1.2.1.21 Patients who have a planned treatment with any other investigational device or procedure during the study period

6.1.2.1.22 Patients planned to undergo any other cardiac surgical or interventional procedure during the TAVI procedure (e.g., concurrent coronary revascularization) or within 10 days prior to the TAVI procedure. NOTE: Diagnostic cardiac catheterization is permitted within 10 days prior to the TAVI procedure.

6.2 Subject Enrollment

6.2.1 Screening and Enrollment

Patients meeting indications for TAVI will be pre-screened for study eligibility by a member of the research team, including a review of the patient's medical history and any existing diagnostic imaging testing that has been performed as a part of the patient's normal medical care.

Based on the results of pre-screening, potentially eligible patients will be asked to provide written informed consent. Informed consent must be documented prior to the performance of any study-specific screening procedures or assessments. Following receipt of informed consent, a baseline screening assessment will be conducted to verify eligibility; the required documentation must also be provided to the Patient Review Committee (§11.1) to determine anatomic eligibility for the trial.

The patient will be considered enrolled in the study when all the following criteria have been met:

- The patient has provided written informed consent
- Baseline screening has been conducted and:
 - The Patient Review Committee has determined that the patient meets the evaluated anatomic eligibility criteria (based on imaging analysis by independent CT core laboratory) AND
 - The investigator has determined that the patient meets all applicable remaining inclusion and no exclusion criteria
- The point of enrollment has been reached:
 - **For evaluable subjects** (Intervention and Control groups), the point of enrollment is the moment of randomization. Randomization will occur:
 - Within 72 hours prior to the scheduled initiation of the TAVI procedure AND
 - After the investigator has confirmed the subject meets all anatomic eligibility criteria
 - **For Roll-In subjects**, the point of enrollment is the introduction of the TriGuard HDH or TriGUARD 3 device into the bloodstream.

A screening log will be completed to document the enrollment and subject number, or reason for non-enrollment of subjects screened but not enrolled in the study. All enrolled subjects are required to complete all assigned follow-up assessments. No single site was permitted to enroll more than 20% of the total number of evaluable subjects (i.e., no single site may enroll more than 57 evaluable subjects in the initial randomized cohort [in addition to any roll-in subjects] in Phase I, and no more than 45 randomized subjects in the initial randomized cohort [in addition to any roll-in subjects] in Phase II).

Randomization will be stratified by implanted valve type (Medtronic vs. Edwards).

No single valve type will be implanted in more than approximately 70% of randomized patients (phase II).

After at least 50% of the patients in the initial randomized cohort (approximately 112 subjects) have reached the 30 day primary efficacy endpoint evaluation time point, a sample size reestimation will be performed in case the conditional power of the trial (assessed by the independent biostatistician) is >40% but <80%, subject to approval by the Sponsor. If this analysis determines that more than 225 randomized subjects will be required to ensure adequate study power, enrollment may continue until the required number of subjects have been enrolled, or until the total subject limit for the study has been reached (whichever occurs first).

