6.2.2 Roll-In Subjects

Sites will enroll a minimum of 2 and a maximum of 3 Roll-In subjects. Roll-In subjects will not be randomized to a treatment arm, but will undergo TAVI with the TriGUARD 3 CEPD and will undergo all protocol-specified follow-ups. These cases will be proctored by a Sponsor representative.

For the purposes of analysis, a subject is considered enrolled in the Roll-In phase of the study when:

- The patient has been judged to meet all inclusion and no exclusion criteria (including approval by the PRC), and has signed a Patient Informed Consent form
- The TriGuard HDH or TriGUARD 3 device has been introduced into the patient's bloodstream

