9.9 Reporting

9.9.1 General Adverse Event Reporting Procedures

Investigators are required to keep records on “all relevant observations, including records concerning adverse device effects (whether anticipated or unanticipated)” according to 21 CFR 812.140. Adverse event collection will occur from the point of study enrollment to study closure. All new or worsening (from baseline) clinically significant adverse events will be captured on the AE CRF through the 90-day follow-up telephone visit. Non-clinically-significant adverse events will not be required post discharge from the initial study procedure. It is the responsibility of the Investigator to assess the subject for adverse events and, if it is determined that a clinically significant AE has occurred, to capture the required adverse event information on the AE CRF. Independent monitoring will be conducted (§14.1) to review source documentation and verify the complete and accurate capturing of adverse events.

The general procedure for investigators reporting any adverse event is as follows:

- If an adverse event occurs, complete all sections of the Adverse Event CRF
- Each unique event/diagnosis must be documented separately
- Documented pre-existing conditions are not considered to be reportable AEs unless there is a change in the nature or severity of the condition
- The AE CRF must be reviewed by the investigator

For adverse events not meeting the criteria for an SAE or (potential) UADE, the sponsor recommends that the Investigator notify the sponsor within 10 working days of first learning of the AE using the electronic data capture (EDC) CRF. If necessary, the Investigator may be requested to provide de-identified copies of source documentation (e.g., physician/nurse notes or summaries) regarding the event.

The Investigator must also notify the responsible IRB/EC regarding new and significant safety information and any events identified by Keystone Heart Ltd. that require expedited FDA or other regulatory authority reporting as serious, unexpected, and related to the investigational device. It is the responsibility of the investigator to ensure site-specific IRB/EC reporting requirement are met.

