12.2 Sample Size Calculation

12.2.1 Hypotheses

12.2.1.1.1 Primary Safety Hypothesis (Phase I and Phase II reported individually)

The primary safety hypothesis is that the rate of the primary safety endpoint (a composite of death, stroke, life-threatening or disabling bleeding, AKI [Stage 2 OR 3], coronary artery obstruction requiring intervention, major vascular complication, and valve-related dysfunction requiring repeat procedure) in the group undergoing TAVI with either protection device system (Intervention Groups) at 30 days will be less in each device group (TriGuard HDH and TriGUARD 3) compared separately to a performance goal (PG) of 34.4%.

Specifically, the primary safety analysis will assess if the Intervention group's safety event rate is significantly less than the PG of 34.4% using a one-sample z-test of proportions. The formal null and alternative hypotheses to be tested are:

$$H_0: \pi \geq 0.344$$

$$H_1: \pi < 0.344$$

where π is the true safety event rate for the Intervention arm.

The primary hypothesis test will be carried out by comparing the upper bound of the one-sided 95% confidence interval of the primary safety endpoint event rate in the intervention arm to the PG. With the planned evaluable sample size of 179 subjects and a one-sided alpha of 0.05, the critical value for rejection of the null hypothesis is 28.5%: if the primary

safety endpoint occurs in 28.5% or less of intervention group subjects, the performance goal will be met.

After accounting for a potential 5% loss to clinical follow-up at 30 days (including subjects who do not meet As Treated population criteria), the total required intervention group sample size is 190 subjects in each Phase. For Phase II 150 subjects randomized to the TriGUARD 3 and the 40-50 roll-ins will constitute the primary safety population.

Trial success depends on both primary endpoints being met in their primary analysis populations; i.e., the primary safety endpoint must be met in the primary (AT) population and the primary efficacy endpoint must be met in the primary (eITT) population in order for the trial to be declared a success. Because both primary endpoints (safety and efficacy) must be met (i.e., both H_0 must be rejected) for the trial to be declared a success, no adjustment to alpha for multiple endpoints is required for the two primary study endpoints.

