12.3.3 As Treated Analysis Population

The As Treated (AT) analysis population is defined by the treatment actually received, rather than the treatment assigned. In the AT population, subjects in whom vascular access in the

contralateral femoral artery has been established for the intended deployment of the TriGuard HDH or TriGUARD 3 device will be analyzed as part of the Intervention group, and subjects in whom the TAVI procedure is initiated (but no vascular access for intended deployment of the TriGuard HDH or TriGUARD 3 is established) will be analyzed as part of the Control group.

The AT population will be used for the primary analysis of all primary and secondary safety endpoints. The AT population will also be used as the secondary analysis population for the secondary performance endpoints and Other Measures.

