12.3.5 Roll-In Patient Population

The Roll-In (RI) patient population is defined as all subjects who undergo TAVI with the TriGuard HDH or TriGUARD 3 prior to enrollment of the first evaluable subject at each investigational site. Each investigational site without prior experience with the TriGuard device (minimum of 2 prior cases) will enroll a minimum of 2 RI subjects. RI subjects will not be randomized to a treatment arm, but will undergo TAVI with the embolic protection device and will undergo all protocol-specified follow-ups.

For the purposes of analysis, a subject is considered enrolled in the Roll-In phase of the study when:

- The patient has been judged to meet all inclusion and no exclusion criteria, and has signed a Patient Informed Consent form
- The TriGuard HDH or TriGUARD 3 device has been introduced into the patient's bloodstream

The RI patient population will be used for a separate analysis of all primary and secondary endpoints and Other Measures. Additional analyses will evaluate primary and secondary endpoints in the pooled population of RI Subjects plus Evaluable Subjects.

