12.4.8 Roll-In Population Analysis

The Phase II Roll-In population will be pooled with the Phase II intervention group for the primary analysis of the primary safety endpoint. The Roll-In patient population will also be

used for a separate analysis of all primary and secondary endpoints and other measures. Additional analyses will evaluate primary and secondary endpoints in the pooled population of Roll-In Subjects plus Evaluable Subjects. The results of all analyses will be reported using descriptive statistics.

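### Roll-ins join the primary safety set only at device entry, randomised subjects from established femoral access, so a roll-in stopped in between is not counted

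*Combined protocol and SAP*

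**What the plan says.** **Roll-in entry.** Section 6.2.1 states that "the point of enrollment is the introduction of the TriGuard HDH or TriGUARD 3 device into the bloodstream". Section 6.2.2 repeats the condition as the rule for analysis: "The TriGuard HDH or TriGUARD 3 device has been introduced into the patient's bloodstream". Section 12.3.5 carries the same condition and defines the population as "all subjects who undergo TAVI with the TriGuard HDH or TriGUARD 3 prior to enrollment of the first evaluable subject at each investigational site".

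**Randomised entry.** For these subjects "the point of enrollment is the moment of randomization", which precedes the procedure. Under section 12.3.3, subjects in whom contralateral femoral access has been "established for the intended deployment of the TriGuard HDH or TriGUARD 3 device will be analyzed as part of the Intervention group". The Synopsis and Appendix I give the same rule. Device entry is not required.

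**Pooling.** Section 12.4.8: "The Phase II Roll-In population will be pooled with the Phase II intervention group for the primary analysis of the primary safety endpoint". Section 12.2.1.1.1: "For Phase II 150 subjects randomized to the TriGUARD 3 and the 40-50 roll-ins will constitute the primary safety population".

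**Adverse events.** Section 9.9.1: "Adverse event collection will occur from the point of study enrollment to study closure". Section 7.5 also documents events from enrollment onward. Table 7a, however, lists adverse events on procedure day 0.

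**The concern.** One single-arm test uses two entry rules. There is a real interval between them. As section 4.3.1.1.2 describes TriGUARD 3, femoral access comes first, the 8F sheath is then advanced over the wire, and the device meets the bloodstream when it is de-sheathed. Access-related injury with serious consequences is a major vascular complication under Appendix I. Major vascular complication and life-threatening bleeding are both components of the primary safety endpoint (section 5.4.1.1).

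A roll-in whose procedure is abandoned in that interval is never enrolled. Section 6.2.1 requires follow-up only of enrolled subjects, so a death, stroke or kidney injury later in the 30 days is missed as well. The tipping-point analysis in section 12.4.2 does not help, because it covers premature withdrawal and not patients who never entered. What is at stake is selective loss of complication-driven aborts among the first device cases at each site, in a comparison with a fixed goal.

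**Working it through.** **1. Inputs.** Performance goal 34.4%, expected rate 25%, 179 evaluable subjects, one-sided alpha 0.05, one-sample z-test, stated critical rate 28.5% and stated power 85% (sections 12.2.1.1.1, 12.2.4.1 and 12.4.2). Safety set: 150 randomised plus 40–50 roll-ins.

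**2. The plan's own figures.**
- Critical rate = 0.344 − 1.645 × √(0.344 × 0.656 / 179) = 0.2856. The largest passing count is 51/179 = 28.49%, which agrees with 28.5%.
- Power = Φ[(0.2856 − 0.25) / √(0.25 × 0.75 / 179)] = 86.4%, close to the stated 85%.
- Allowing 5% loss: 179 / 0.95 = 188.4, so 189 against the stated 190.

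The design figures are not in dispute.

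**3. Roll-in share.** 40/190 = 21%; 50/200 = 25%.

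**4. Who is counted.**

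| Course of the procedure | Randomised to device | Roll-in |
|---|---|---|
| Access not established, TAVI initiated | As Treated Control, so outside the test | Not enrolled, so outside the test |
| Access established, device never enters | Intervention, counted | Not enrolled, so outside the test |
| Access event, then device enters | Counted, event included | Counted; the text conflicts on whether the event is collected |
| Device enters, then event | Counted | Counted |

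Only the second row is a definite asymmetry. The third is an unresolved conflict between sections 9.9.1 and 7.5 on one side and Table 7a on the other.

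**5. Effect at the pass boundary.** z = (x/n − 0.344) / √(0.344 × 0.656 / n), restoring omitted roll-ins who all had an event:

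| Restored events | x/n | Rate | z | One-sided p |
|---|---|---|---|---|
| 0 | 51/179 | 28.49% | −1.664 | 0.048 |
| 1 | 52/180 | 28.89% | −1.556 | 0.060 |
| 2 | 53/181 | 29.28% | −1.450 | 0.074 |

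A restored roll-in without an event moves the rate the other way: 51/180 = 28.3%.

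**6. Effect from the planned rate.** 0.25 × 179 = 44.75, taken as 45. Eight restored events give 53/187 = 28.34%, against a critical rate of 0.344 − 1.645 × √(0.344 × 0.656 / 187) = 28.69%, which still passes. Nine give 54/188 = 28.72%, against 28.70%, which fails.

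**7. Type I error under an assumption.** Suppose a fraction q of roll-in attempts have an endpoint event before device entry and drop out, no event-free roll-in drops out, and the true rate over all attempts is 34.4%. The recorded roll-in rate is (0.344 − q)/(1 − q). This is weighted with 0.344 for randomised subjects by the roll-in share, and the 28.56% critical rate is applied at n = 179. For 40–50 roll-ins the nominal 5.0% becomes 5.8–6.0% at q = 2%, 7.4–7.9% at q = 5%, and 11.0–12.6% at q = 10%. The documents support no particular q.

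**The case against.** The best defence is that the As Treated rule already covers roll-ins. Section 12.4.2 says the As Treated analysis includes them, and Appendix I assigns all subjects with established access to Intervention. That reading is possible. However, section 6.2.2 states its device-entry rule expressly for analysis, a roll-in is not an enrolled subject before that point, and no section restores one who stops earlier. The ambiguity itself needs to be resolved.

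Three stronger readings are tempting, and the documents do not support them.

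- *Failed access is counted for randomised subjects but lost for roll-ins.* As Treated requires access to be established. A randomised subject without it, once TAVI is initiated, is analysed as Control and also leaves the test.
- *No adverse events are recorded for roll-ins before device entry.* Table 7a lists them on day 0, and section 12.4.9 treats events starting during the index procedure as treatment-emergent. For a roll-in who goes on to receive the device, the plan is in conflict; it does not settle on exclusion.
- *One omitted event would overturn the safety result.* That is true only at 51/179.

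It is also fair that the omitted patient leaves a trace, because section 6.2.1 requires a screening log with the reason for non-enrollment. The patient is traceable but not analysed. Finally, the secondary ITT safety analysis as the Synopsis describes it excludes roll-ins and is untouched, although section 12.4.2 says roll-ins are included there too.

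**Conclusion.** The point holds for one narrow group: roll-ins with established contralateral femoral access whose device never enters the bloodstream. As written, the plan leaves them out of the test against 34.4% and counts randomised subjects with the same course.

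The bias favours the device if the event rate among the omitted roll-ins exceeds that among those counted. That is likely when a complication caused the abort, but it is not established for aborts in general. The documents give neither the number omitted nor their event rate, so the size is unknown and probably small. The boundary figures and the type I error range rest on assumed counts and treat every omitted subject as an event. The sample size, power and critical rate are not themselves wrong. The case for acting is that the gap is selective, affects a component of the set that is 21% to 25% of the total, and is cheap to close.

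**What to change.** - In sections 6.2.1, 6.2.2 and 12.3.5, set roll-in entry for the safety analysis at established contralateral femoral access for intended deployment, matching section 12.3.3.
- State in sections 9.9.1 and 7.5 that roll-in adverse events are collected from that point, consistent with Table 7a.
- Follow all such roll-ins to 30 days and include them in the primary safety analysis.
- For roll-ins already attempted, use the screening logs to identify those who had access but no device entry, and report a sensitivity analysis that includes them.

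The cost is protocol wording, a few extra case report forms and possibly a slightly less favourable safety rate. The change does not capture failed access, nor does it need to, since that is already treated alike in both groups.
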